In a pilot survey ([name] as PI), we found poor breastfeeding knowledge among 21 pregnant and 18 postpartum women who quit smoking during pregnancy. Only 28.6% agreed "Babies should be exclusively breastfed for the first 6 months (current clinical guidelines)", 52.4% agreed "The best way to feed a baby is breastfeeding", and 38.1% agreed "If a baby is breastfed he or she will be less likely to get diarrhea". Their intention to breastfeed was also relatively low: only 42.9% planned to breastfeed exclusively in the first weeks after delivery, and only 9.5% planned to exclusively breastfeed for 6 months. Their actual breastfeeding practice was even lower: only 22.2% and 0% breastfed exclusively in the first week and 6 months after delivery, respectively. Quitters tend to wean their infants sooner than nonsmokers, and their breastfeeding rate at 4 months postpartum is similar to that of continuous smokers'. These consistent data suggest an urgent need to promote breastfeeding among women who quit smoking during pregnancy. One of our key team members, [name] (Co-I), has developed, tested, and published a highly effective intervention funded by NIH to increase breastfeeding duration among low income mothers. For instance, the breastfeeding rate at 6 months postpartum was 72% in the intervention group, compared to 0% in the usual care group. We plan to modify her intervention to promote breastfeeding among ex-smoking mothers in the proposed project.

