**Component# 2 - Postnatal lactation counseling:** A part-time CLC will be hired to provide timely and individualized postnatal lactation counseling. She will monitor each participant's breastfeeding progress, help them initiate breastfeeding immediately after delivery, correct myths and flaws, answer questions, and offer suggestions and tips to solve potential problems. Besides face-to-face meetings, text messages and phone calls will also be used to provide timely assistance of lactation practice and routine checking of feeding status.

**Component #3 - Family/Peer/Employer support:** The participant will nominate a family supporter for her breastfeeding. The family supporter will receive our training for skills in supporting the participant's decision and effort to breastfeed. Other family members will also receive a breastfeeding support booklet. The PI has successful experience of training 16 family supporters for our Pregnancy and Smoking Cessation Study. In addition, we will encourage participants to attend Buffalo's Baby Cafés (6 sites), a breastfeeding drop-in support group, to seek further support from lactation counselors and other breastfeeding mothers (peers). Particularly, the PI has been collaborating with one of these sites, the Durham's Central City Baby Café (see **Letter of Support**). This Baby Café has been helping 214 of 221 mothers (96.8%) to breastfeed successfully since 2013. A booklet on benefits of breastfeeding for business, how to support a nursing mother in workplace, laws and policies of promoting breastfeeding will be available to the participant's employer.

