**Component #4 - Contingent financial incentives:** Participants will receive incentives for breastfeeding if they are able to nurse or to provide milk by pumping in the presence of a female research staff. In the Co-I [name] effective intervention (e.g., 72% breastfeeding rate at 6 months postpartum vs. 0% usual care), contingent incentives start at \$20 at the end of first month and increase by \$10 every month until the end of 6 months postpartum. We will adapt this incentive schedule for the proposed project by adding two home visits in week 1 and week 2 postpartum for breastfeeding consultation with \$20 incentive for breastfeeding, given that the first month postpartum is critical to address high risk of breastfeeding discontinuation and smoking relapse. The family supporter will also receive \$10 incentive/month if the participant is still breastfeeding.

**Component #5 - Early limited formula milk (ELF) via syringe:** This component is optional and is only reserved for at-risk infants with 5% or more birth weight loss within the first 2 days of life when the mother decides to add formula. The goal of ELF is to ensure supplemental use of formula to help the at-risk infant grow but will not interrupt the success of breastfeeding. Specifically, the mother should always breastfeed the infant first. If needed, a limited amount (10.0 mL or less) of formula milk is then complemented. The formula milk is administered via syringe rather than baby bottles, which can prevent nipple confusion. ELF will be discontinued once breast milk can meet the infant's need, usually within 2 weeks. ELF has been shown to increase exclusive breastfeeding rate (79% vs. 42% usual care) at 3 months postpartum for at-risk infants.

**b) Control Group.** Participants in the control group will receive a brief pamphlet on the benefits and skills of breastfeeding. They will complete the same frequency of study visits as the intervention group to monitor their feeding plan/practice with a fixed compensation (\$15/visit), regardless of feeding practice.

**c) Fidelity and quality control.** Step-by-step instructions will be used for each visit. The PI will train all research staff. Evaluation will be conducted via exams and trial runs before their interacting with participants. All visits will be audio-recorded for quality assurance and 20% of audio files will be reviewed by the PI.

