**Comments.** We decided not to include any education or intervention directly targeting on smoking relapse. This will allow us to test the independent effect of breastfeeding promotion on smoking relapse.

**3.1.7 Follow-up.** To evaluate sustainability of the effects of breastfeeding promotion on smoking relapse, we will follow participants and infants in 9 months postpartum (i.e., 3 months after breastfeeding intervention ends).

**3.1.8 Outcome measures.** The key outcome measures include timing of postpartum smoking relapse (primary) and breastfeeding duration (secondary) derived from data repeatedly collected throughout the study (**Table 1**). Outcomes will be assessed by graduate research assistants who are blinded to group assignments.

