*Maternal negative affect.* Maternal negative affect will be measured at enrollment and all postpartum visits using the Positive and Negative Affect Schedule (PANAS). The 10 items on negative affect include being distressed, upset, guilty, ashamed, hostile, irritable, nervous, jittery, scared, and afraid. Participants will rate their experience of each particular emotion in the past few weeks. With this time frame, its Cronbach's alpha was 0.87 and test-retest reliability was 0.48. In addition, we will measure maternal anxiety with the State-Trait Anxiety Inventory and postpartum depression with the Edinburgh Postnatal Depression Scale.

**3.1.10 Covariates.** We consider partner smoking, maternal secondhand smoke exposure, education, household income, health motivation, perceived social support, as covariates. They may confound our results and will be controlled in data analysis if not comparable between intervention and control groups.

**3.1.11 Economic costs.** We will collect information on intervention (not research and development) costs such as personnel, recruitment, materials, compensation, incentives, and transportation. We will include outcome costs for formula, medical care of NICU stay and sick child visits, and parental absenteeism for infant illness.

**3.1.12 Statistical Analysis.** *Specific Aim 1 (Breastfeeding promotion and postpartum smoking relapse).* The timing of postpartum smoking relapse (outcome) will be analyzed with Cox regression model by including group assignment (intervention vs control), smoking status (1=smoking, 0=non-smoking), the observed time, and significant covariates. The proportional hazard ratio of postpartum smoking relapse between two groups will be calculated. We will estimate Kaplan-Meier survival curves to visually compare smoking trajectories. Intent-to-treat analysis will be used with all randomized participants being included in their originally assigned groups. Dropouts, losses to follow-up, fetal deaths, and miscarriages will be coded as missing data on smoking status. If missing data on smoking status is more than 20%, we will run pattern mixture models and sensitivity analyses. A supplemental analysis will be run to examine *prenatal* smoking relapse during pregnancy.

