*Specific Aim 2 (Mediation analyses on mechanisms).* We will use dynamic path analysis to examine the mechanisms through which breastfeeding reduces smoking relapse. The dynamic path analysis includes simultaneous fitting of the Aalen additive hazards model (the R package 'timereg') and ordinary path analysis (PROC TCALIS in SAS). It fits our survival data with internal time-dependent mediators (e.g., oxytocin or prolactin) and a counting process as the outcome (i.e., smoking relapse). Hormonal baseline level and response to infant feeding (oxytocin or prolactin) will be included into the model as independent mediators. We will estimate the direct, indirect (through one or multiple mediators), and total effects of breastfeeding on smoking relapse (**Figure 1**). The PI has sufficient experience in mediation analysis.

**3.1.13 Sample size.** According to the literature, we estimate 45% rate of smoking relapse by 6 months postpartum in the control group. Assuming 45% protection effect of breastfeeding against postpartum smoking relapse, we estimate 25% (45%\*[1-45%]) rate of smoking relapse by 6 months postpartum in the intervention group. The corresponding sample size is 98 per group with type 1 error  $\alpha$  of 0.05 and power  $1-\beta$  of 0.8 to detect significant difference in smoking relapse between two groups in the larger R01 project. If 9-month postpartum smoking relapse rates (70% control vs 39% intervention) are used, the corresponding sample size is 46 per group. Therefore, 30 participants per group for this pilot study should provide sufficient sample size to test feasibility and efficacy as well as provide preliminary data regarding mediators and cost-effectiveness.

**3.2 Potential Problems & Alternative Strategies.** A potential challenge for the proposed project is to recruit a sufficient number of pregnant ex-smokers. If significant delay is observed, we will expand recruitment areas, use direct mailing, and advertise in local media. Another potential problem is attrition during intervention and follow-up periods. We expect 20% attrition rate due to dropouts, losses to follow-up, miscarriages, and fetal deaths. If we lose contact, we will reach out to the 3 people that have close relationship with the participant indicated at enrollment. We will recruit more participants to ensure sufficient statistical power if attrition is high.

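### Aim 2 estimates effects of breastfeeding with no stated term for randomised arm, so part of any package effect that bypasses breastfeeding would be credited to breastfeeding

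*Combined protocol and SAP*

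**What the plan says.** In section 3.1.12, Specific Aim 2 uses dynamic path analysis "to examine the mechanisms through which breastfeeding reduces smoking relapse". Its targets are stated as: "We will estimate the direct, indirect (through one or multiple mediators), and total effects of breastfeeding on smoking relapse". The only mediators that the Aim 2 text places in the model by name are hormonal: "Hormonal baseline level and response to infant feeding (oxytocin or prolactin) will be included into the model as independent mediators". For the paths it points to Figure 1, which is not reproduced in the text available for review. It gives no arm term, no adjustment set, and no definition of the breastfeeding variable (yes/no, duration, or status over time).

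Aim 1, in the same section, does place arm in its Cox model: "by including group assignment (intervention vs control), smoking status (1=smoking, 0=non-smoking), the observed time, and significant covariates".

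Section 3.1.6 describes what separates the arms. The intervention arm has group education, individual lactation counselling with texts and calls, contingent cash, peer and employer support, an optional feeding component for at-risk infants, and a nominated supporter: "The family supporter will receive our training for skills in supporting the participant's decision and effort to breastfeed". For controls: "Participants in the control group will receive a brief pamphlet on the benefits and skills of breastfeeding". Controls attend equally often and receive the same fixed $15 per visit. The Comments in 3.1.6 explain why no smoking content is included: "This will allow us to test the independent effect of breastfeeding promotion on smoking relapse".

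Section 3.1.10 lists six covariates, perceived social support among them, to be adjusted for when the arms are not comparable. Randomised arm is not on that list.

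**The concern.** Randomisation protects a comparison by arm. It does not protect a comparison by breastfeeding status. Counselling, a trained supporter and extra money could each plausibly ease stress or negative affect, or reduce relapse, whether or not the mother breastfeeds. Stress, negative affect and bonding are among the plan's own mediators (3.1.9, Table 1). Arm is therefore a plausible common cause of breastfeeding, of several mediators and of relapse. If it is left out, the breastfeeding terms pick up part of its effect.

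At stake is the mechanistic claim. Section 3.1.13 offers preliminary data on mediators, and section 3.4 says the pilot data will support a larger grant application. An effect of support or attention could then be presented as an effect of breastfeeding, and the next trial would be built on a mechanism that this analysis did not isolate.

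**Working it through.** The plan gives no numerical figure for Aim 2, so there is none to reproduce. Its sample sizes (98 and 46 per group) do reproduce with a two-sided, continuity-corrected comparison of proportions, but they do not bear on this point.

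**Inputs.** Allocation is 30:30 (3.1.5). Breastfeeding rates cited by the plan:
- From section 1: "the breastfeeding rate at 6 months postpartum was 72% in the intervention group, compared to 0% in the usual care group".
- From 3.1.6, Component #5: 79% versus 42%, exclusive, at 3 months, at-risk infants.
- From the pilot survey in section 1: 22.2% exclusive in week 1, used here as an illustrative control rate.

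A control rate of 20% is an assumption.

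**Step 1: share credited to breastfeeding when arm is omitted.** Suppose the package changes relapse by an amount d that does not depend on breastfeeding, and breastfeeding has no effect. In a linear model with breastfeeding only, the breastfeeding coefficient is d × [P(intervention | breastfeeding) − P(intervention | not breastfeeding)]. With rates p1 and p0 and equal arms:

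share = p1/(p1+p0) − (1−p1)/(2−p1−p0)

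| Rates (intervention/control) | Calculation | Share |
|---|---|---|
| 72/0 | 1.000 − 0.28/1.28 = 1.000 − 0.219 | 78% |
| 72/20 (assumed control rate) | 0.783 − 0.259 | 52% |
| 72/22.2 | 0.764 − 0.265 | 50% |
| 79/42 | 0.653 − 0.266 | 39% |

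With 72% in the intervention arm, the share drops below one half once control breastfeeding reaches about 23%.

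The formula is exact for a linear model. In an additive hazards model it is approximate, because the arm mix among women still at risk drifts over time. As a check, trials were simulated with 30 per arm and no breastfeeding effect, with 9-month relapse of 70% in controls and an assumed 55% under support alone. The additive hazards model without arm credited breastfeeding with about 72% to 78% at 72/1 and 50% to 54% at 72/20. The formula gives 77% and 52%.

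**Step 2: which path receives it.** A large simulated linear path model at 72/0 had no true breastfeeding or hormone effect on relapse.
- Hormones depend on arm only through breastfeeding, and none of the package effect acts on stress: all 78% goes to the direct breastfeeding path and about 0% to hormones.
- The same, but half the package effect acts through stress or bonding: about 38% direct, 40% through stress or bonding, about 0% through hormones.
- Arm also shifts hormones at fixed breastfeeding status, by an assumed 0.5 to 1 times the breastfeeding effect on the hormone: 3.5% to 17% through hormones at 72/0, and up to 24% at 72/22.2 or 79/42.

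**Step 3: what an arm term does and does not remove.** With arm in every equation, the wrongly credited share falls to about 0 for effects that do not depend on breastfeeding. Contingent cash is different. It is up to 20+20+20+30+40+50+60+70 = $310 for the mother, plus $10 a month for the supporter, and both are paid only while she breastfeeds. Such an effect exists only among breastfeeding women in the intervention arm. The part left on breastfeeding after arm adjustment is p1(1−p1) / [p1(1−p1) + p0(1−p0)]:
- 72/0: 0.2016/0.2016 = 100%
- 72/22.2: 0.2016/(0.2016+0.1727) = 54%
- 79/42: 0.1659/(0.1659+0.2436) = 41%

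At 72/0 no control breastfeeds, so the adjusted effect is identified only within the intervention arm: about 30×0.72 = 21.6 women against 8.4.

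**Step 4: price in precision.** The squared arm–breastfeeding correlation is φ² = (p1−p0)² / [4·p̄(1−p̄)], where p̄ is the mean of the two rates. The standard error grows by 1/√(1−φ²).

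| Rates | φ² | Standard error ratio |
|---|---|---|
| 72/0 | 0.5625 | 1.51 |
| 72/20 | 0.272 | 1.17 |
| 79/42 | 0.143 | 1.08 |

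**The case against.** Several points on the other side carry weight.

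- **Silence is not exclusion.** Aim 2 refers its paths to Figure 1, which cannot be seen. A reader might infer that arm is definitely left out. The text supports only that no arm term is stated, in contrast to Aim 1. The account of the conceptual model in section 1 does begin with suckling rather than assignment.
- **Hormones.** A reader might infer that oxytocin and prolactin would be wrongly credited with the package's effect. Step 2 does not support that. It happens only under an added assumption, for example when a yes/no variable hides differences in exclusivity.
- **Most of the effect.** That holds at 72% versus 0%, which is another study's 6-month result and not a projection for this trial. The 79% versus 42% and 22.2% figures are themselves for exclusive breastfeeding at other times. The share should be given as a range.
- **Matched contact.** Controls have the same visit frequency and payment, so attention is partly balanced. What differs is the content of contact, the supporter and the contingent cash.
- **The covariate rule.** A reader might take 3.1.10 to be confined to baseline variables. It does not say so, and an imbalance in perceived social support might be adjusted for. Even so, the rule does not name arm, and support is only one of the differences.
- **The Comments in 3.1.6.** These claim an independent effect of breastfeeding promotion, not of breastfeeding itself. That is compatible with a package test and is not an error.
- **Scale.** Aim 2 is preliminary work in 60 women, and no significance test is stated for it. This limits the harm but does not make the stated estimand right.

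**Conclusion.** The point holds in limited form. As written, Aim 2 would credit to breastfeeding roughly 39% to 78% of any package effect that bypasses it, on the rates the plan cites. The excess falls on the direct path and on stress, affect and bonding. This assumes an additive package effect that is the same whatever the feeding status, a binary breastfeeding variable fixed per woman, and no arm term in the unseen figure. The documents give no basis for the size of such a package effect, so no absolute bias or false-positive rate is claimed.

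A reader might also infer that adding arm isolates the effect of breastfeeding. It does not. Cash conditional on breastfeeding stays attached to it, and women within an arm still choose whether to breastfeed. Aim 1 is unaffected as a randomised test of the multicomponent package. The change should be made before analysis because the mechanism findings are meant to support the next grant.

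**What to change.** In 3.1.12, Specific Aim 2:

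1. Make randomised arm the first node and the exposure for the total effect, so that the total effect remains a randomised comparison. Place breastfeeding as the first mediator, with hormones, bonding, interaction, stress and affect downstream. Keep arm in every equation.
2. Define the breastfeeding variable, for example as time-varying status. Table 1 already collects it at every postpartum visit.
3. Report the arm-adjusted breastfeeding paths as observational and exploratory. State that they still contain any effect of cash paid only to breastfeeding mothers and any self-selection within arm, and that with no breastfeeding among controls they are identified only within the intervention arm. The arm path that bypasses breastfeeding needs the same label, since it conditions on a behaviour after randomisation.

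The cost is SAP wording and one extra term per equation, with no new data. The standard error of the breastfeeding coefficient rises by about 1.5 times at 72% versus 0%, 1.2 times at 72% versus an assumed 20%, and 1.1 times at 79% versus 42%.

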### **3. Approach**

**3.1 Research Design.** **3.1.1 Overview.** This is a randomized controlled trial to prevent postpartum smoking relapse by breastfeeding promotion. The intervention group (N=30) will receive multicomponent breastfeeding intervention from late pregnancy to 6 months postpartum, while the usual care control group (N=30) will only receive minimum breastfeeding education. The key outcome is the timing of postpartum smoking relapse.

**3.1.2 Recruitment.** We will recruit 60 pregnant ex-smokers from Erie County and Niagara County, NY. Recruitment flyers will be distributed around the communities (e.g., churches, bus/subway stops, laundromats, grocery stores, thrift stores, community centers) and organizations providing basic services (e.g., social services, WIC, job training) to low income pregnant women. Recruitment flyers will also be displayed in 4 large city OB/GYN clinics. Health professionals at these clinics will pass our recruitment materials to ex-smoking patients. We will also send an invitation letter to potentially eligible pregnant women in these clinics. The PI has successful experience in recruiting 50 pregnant smokers for his NIH funded study on smoking cessation during pregnancy over 6 months from 2 obstetric clinics (see **Letters of Support** from clinics). Social media such as Facebook will also be used. Assuming a rate of 23% maternal smoking at conception and 54% smoking cessation rate during pregnancy, we estimate 1,490 out of about 12,000 newborns will be born to mothers who quit smoking during pregnancy within 1 year in the two counties. We assume 60% of these mothers (N=894) will be exposed to recruitment materials, and then 30% (N=268) are interested in this project. Therefore, it is feasible to recruit 72 (60 + 20% attrition) eligible participants within 1 year.

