**Figure 1. Conceptual Model for Breastfeeding and Smoking Abstinence\***

\* Other hormonal mechanisms, such as progesterone, estrogen, ACTH, cortisol, and tetraiodothyronine (T4), will be included in the larger R01 grant.

must be at 28 weeks of pregnancy or earlier to ensure adequate time for prenatal breastfeeding intervention. Exclusion criteria are teen pregnancy (<18 y); current use of other tobacco or nicotine products; medical conditions contraindicating breastfeeding such as HIV infection, active tuberculosis, and breast removal; current heavy drinking (more than 2 drinks a day); current use of other psychoactive substances; being strongly against breastfeeding; and non-English speakers. To increase the possibility to obtain a representative sample of the generable population, the study will be advertised as a program to promote healthy infant feeding among pregnant women without requiring breastfeeding intention or mentioning smoking relapse prevention. We will not exclude women without current intention to breastfeed (28.6% in our pilot survey), unless they are strongly against breastfeeding (4.8%). Similarly, we will not exclude women who plan to relapse after delivery (0% in our pilot survey), as our breastfeeding promotion may motivate them to maintain abstinent for a longer period especially if they know tobacco metabolites are concentrated in breast milk.

**3.1.4 Pre-test visit.** During this visit, we will measure the participant's urine cotinine, height, and body weight. Participants will complete a survey on smoking temptations, nicotine dependence before quitting, smoking cessation history, self-efficacy to maintain smoking abstinence, smoking environment including partner smoking behaviors, breast health, breastfeeding knowledge, breastfeeding history, relationship with partner and other family members, social network, stress, negative affect, physical activity, sleep, and diet.

**3.1.5 Randomization.** At 28 weeks of pregnancy, eligible participants will be randomized into either the intervention group (N=30) or the control group (N=30) using a sequence of random numbers in blocks of 2, which can ensure equal or close numbers of participants between the two groups throughout the project.

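### Section 3.1.13 calls 30 per group sufficient to test efficacy, although its own 80%-power figure on this trial's 9-month rates is 46; power at 30 is about 68–72%

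*Combined protocol and SAP*

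**What the plan says.** All references are to the combined protocol and SAP.

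- **Section 3.1.13, 6-month rates (45% vs 25%).** "The corresponding sample size is 98 per group with type 1 error" 0.05 and power 0.8, and this is "to detect significant difference in smoking relapse between two groups in the larger R01 project".
- **Section 3.1.13, 9-month rates.** "If 9-month postpartum smoking relapse rates (70% control vs 39% intervention) are used, the corresponding sample size is 46 per group".
- **Section 3.1.13, conclusion.** Presented as following from those two figures: "30 participants per group for this pilot study should provide sufficient sample size to test feasibility and efficacy". No power is given for 30 per group.
- **Section 3.1.12.** "The timing of postpartum smoking relapse (outcome) will be analyzed with Cox regression model", by intent to treat, with Kaplan-Meier curves for visual comparison.
- **Section 3.1.7.** "we will follow participants and infants in 9 months postpartum".
- **Section 3.1.2.** "it is feasible to recruit 72 (60 + 20% attrition) eligible participants within 1 year". Section 3.1.5 randomises 30 + 30.
- **Section 3.2.** Expects 20% attrition, places it in the intervention and follow-up periods, and promises further recruitment to protect power if losses are high. It gives no number.

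**The concern.** The section sets a standard (two-sided 5% is implied, power 80%), works out what that standard requires, and then declares a smaller number adequate. Thirty is about two thirds of 46 (30/46 = 65%) and under a third of 98 (30/98 = 31%). The 46 is the fairer comparison, since it uses this trial's own follow-up horizon and the 98 is assigned to the R01.

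A pilot need not be powered for efficacy. The difficulty is that this one says it is, and the sentence lists efficacy among the things to be tested, apart from the preliminary data on mediators and cost-effectiveness. Section 3.4 says the results will support the R01 application. A reader who accepts the claim could take a non-significant hazard ratio as evidence against the intervention, when on the plan's own assumptions such a result is quite likely even if the intervention works as hoped.

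**Working it through.** **Inputs.** Section 3.1.13: relapse rates 45% vs 25% (6 months) and 70% vs 39% (9 months), α = 0.05, power 0.80, 30 per group. Section 3.1.12: Cox regression. Section 3.2: 20% attrition. Sidedness is not stated; two-sided reproduces the plan's figures. The hazard ratio is not stated and is derived below.

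**1. Reproduce the plan's figures.** Two-proportion formula, with d = p₁ − p₂ and p̄ the mean rate:

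n₀ = [1.960·√(2p̄(1−p̄)) + 0.842·√(p₁(1−p₁) + p₂(1−p₂))]² / d²

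with continuity correction n = (n₀/4)·[1 + √(1 + 4/(n₀d))]².

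- 45% vs 25%: n₀ = 88.1, n = 97.8, so 98.
- 70% vs 39%: n₀ = 39.3, n = 45.5, so 46.

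Both match, so the inputs and method are read correctly. The same formula at n = 30 gives power of 58% (9 months) and 27% (6 months).

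**2. Use the planned analysis instead.** An unadjusted Cox test behaves like a log-rank test, so Schoenfeld's formula applies. Under proportional hazards HR = ln(1−p₂)/ln(1−p₁). Events needed for 80% power = 4(1.960 + 0.842)²/(ln HR)². Events expected = n(p₁ + p₂).

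- 9 months: HR = ln 0.61/ln 0.30 = 0.411. Events needed 39.6; 39.6/1.09 = 36.3, so 37 per group.
- 6 months: HR = ln 0.75/ln 0.55 = 0.481. Events needed 58.7; 58.7/0.70 = 83.8, so 84 per group.

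**3. Power at 30 per group.** Power = Φ(|ln HR|·√events/2 − 1.960).

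- 9 months: events = 30 × 1.09 = 32.7; Φ(0.890 × 5.718/2 − 1.960) = Φ(0.585) = 72%.
- 6 months: events = 30 × 0.70 = 21; Φ(0.731 × 4.583/2 − 1.960) = Φ(−0.284) = 39%.

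Checks by simulated log-rank test (20,000 runs): with one constant hazard per arm, 71% and 37%. With hazards constant within 0–6 and 6–9 months and matched to all four rates, 68% and 38%. In the second model the hazard ratio moves from 0.48 to 0.34 after 6 months, so hazards are not proportional. Freedman's formula gives 67% and 36%, and 41 rather than 37 per group at 9 months.

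**4. Attrition, 9-month power.** Simulated values use the two-period hazards.

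| Reading | Simulated | Schoenfeld |
|---|---|---|
| 60 randomised, 20% lost before delivery (24 per group) | 58% | 62% |
| 60 randomised, 20% lost uniformly over 9 months, censored | 63% | – |
| 72 randomised, 20% lost before delivery (about 29 per group) | 66% | 71% |
| 72 randomised, 20% lost uniformly over 9 months, censored | 70% | – |
| Losses precede randomisation, 60 followed fully | 68% | 72% |
| 72 randomised, no loss (36 per group) | 75% | 79.6% |

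**5. The allowance.** 72 × 0.8 = 57.6, so 72 less 20% leaves about 58. Retaining 60 needs 60/0.8 = 75.

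**6. Precision at 30 per group.** With 32.7 events, SE(ln HR) ≈ 2/√32.7 = 0.350, so the 95% CI around 0.41 is 0.41 × exp(±1.96 × 0.350), about 0.21 to 0.81.

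**The case against.** - **It is only a pilot.** Its feasibility and preliminary-data aims need no power calculation. That is right and nothing here disputes them, but the plan itself claims sufficiency for efficacy and draws the claim from power calculations.
- **Nothing is miscalculated.** True: 98 and 46 are correct. The fault lies in the inference from them to 30.
- **46 is not the figure for the planned test.** This stands. The shortfall against the Cox requirement is smaller, 30 against about 37 to 41.
- **No 6-month Cox analysis is planned, and 98 belongs to the R01.** This also stands, so the 6-month power is context only.
- **The log-rank test is a stand-in.** The plan specifies Cox with covariates. The powers here are for the unadjusted comparison.
- **Rounding.** Applying 45% protection to 70% gives 38.5%, shown as 39%. At 38.5%, Schoenfeld power is 73% at 30 per group and 81% at 36. But the plan states 39%, its 46 reproduces only with 39% (38.5% gives 45), and 36 per group reaches 80% only if all 72 women are randomised and none are lost.
- **The hazard ratio is inferred.** Section 3.1.13 applies the 45% protection to cumulative rates, which supports 0.41. Reading it as HR 0.55, with events kept at the stated rates, lowers power to about 40% at 9 months and 28% at 6, so the reading used here favours the plan.
- **The 72 can be read coherently.** 60 × 1.2 is 72, and section 3.1.8 removes women who relapse before randomisation, so 72 recruited could become 60 randomised. Section 3.2, however, places attrition after that point. This is a minor clarification.

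**Conclusion.** The concern holds. By the plan's own calculation 30 per group does not give 80% power for efficacy, and it does not under the planned Cox analysis either. With full follow-up the chance of missing the assumed effect is about 28–32% on the 9-month rates, against the 20% in the plan's formula. After 20% attrition it can reach about 42%. A significant 9-month result is still more likely than not; only an analysis stopped at 6 months would more probably be non-significant, missing the effect about 61–63% of the time.

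These figures assume a two-sided 5% test, the stated relapse rates, hazard ratios derived from those rates, no covariate adjustment and, for the attrition range, the loss patterns shown. On the stated rates, none of the readings examined reaches 80% unless the unquantified top-up brings the trial to at least 37 per group with full follow-up (Schoenfeld; Freedman asks for 41). This should be fixed, but it does not threaten the pilot's feasibility or estimation aims.

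**What to change.** **Needed.** In section 3.1.13, replace the concluding sentence with wording such as: *Thirty per group is chosen for feasibility and to estimate relapse rates and the hazard ratio with a 95% confidence interval; the pilot is not powered at 80% to test efficacy.* Add the Cox power at 30 per group with its assumptions: about 68–72% on the 9-month rates, about 37–39% if 6-month rates are quoted, and the value after expected attrition.

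**Useful clarifications.**

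- State whether 60 or 72 women are randomised.
- Correct the allowance: 72 less 20% leaves about 58, and retaining 60 takes 75.
- In section 3.2, say what power the top-up is meant to protect and how many women it could add.

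**Cost.** Wording only. The efficacy claim becomes less favourable; design, analysis and enrolment do not change.
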